7.6 Interim Analyses

There is no planned interim analysis.

7.7 Additional Analysis/Inference for US FDA

Analyses are as described in all preceding sections except for the items described below.

7.7.1 Primary Efficacy Analyses

There are 2 co-primary endpoints: the average grade change from baseline in the MAS-B of the principal muscle group at weeks 4 and 6 and the average CGI by Physician at weeks 4 and 6. For both co-primary endpoints, the statistical null hypothesis is that both the higher dose (6 U/kg) and the lower dose (3 U/kg) have the same mean as placebo. The alternative hypothesis is that at least one study dose has a different mean than placebo. In addition to the primary statistical analyses cited in Section 7.3.1 for the average grade change from baseline in MAS-B score of the principal muscle group at weeks 4 and 6, the average CGI by Physician at weeks 4 and 6 will be analyzed using the same statistical method (with the same ANCOVA model and the MI method).

The Hochberg procedure ([Hochberg and Tamhane, 1987](#)) will be used to control the family-wise type I error rate. With 2 doses and 2 co-primary endpoints in each dose, the maximum p value for the 2 co-primary endpoints in each dose will be used in the Hochberg procedure. We first define the following values:

- p11: p value for Botox 6 U/kg vs placebo comparing MAS-B
- p12: p value for Botox 3 U/kg vs placebo comparing MAS-B
- p21: p value for Botox 6 U/kg vs placebo comparing CGI
- p22: p value for Botox 3 U/kg vs placebo comparing CGI
- p1 = max(p11, p21), p2 = max(p12, p22).

p1 and p2 will be sorted in an increasing order to get $p(1) \leq p(2)$. The following decision rule will then be applied:

Step 1: If $p(2) \leq 0.05$, both doses are considered efficacious; otherwise go to step 2.

Step 2: If $p(1) \leq 0.025$, its corresponding dose is considered efficacious; otherwise go to step 3.

Step 3: Neither dose is considered efficacious.

For sensitivity analysis purposes to supplement the co-primary analyses, MMRM with unstructured covariance matrices will be conducted for the co-primary endpoints of MAS-B and CGI. The models will include a covariate of baseline MAS-B and factors of age group, principal muscle group, treatment group, visit, treatment-by-visit interaction, study center, and previous botulinum toxin exposure. A summary of the percentages of missing MAS-B and CGI scores by visit will also be provided. Additional sensitivity analyses for the MAS-B

changes from baseline and CGI scores at each assessment time point will also be performed using ANCOVA with the same model as specified for the primary analysis, and linear contrasts will be used to estimate the treatment differences between each study dose and placebo. The sensitivity analyses will be conducted using observed data.

8. Study Visit Schedule and Procedures

Please see Table 1 for a schematic of the schedule visits and procedures.

8.1 Patient Entry Procedures

8.1.1 Overview of Entry Procedures

Prospective patients as defined by the criteria in Sections 4.3 and 4.4 (inclusion/exclusion criteria) will be considered for entry into this study.

8.1.2 Informed Consent and Patient Privacy

The study will be discussed with the patient/legally authorized representative and a patient wishing to participate or his/her legally authorized representative must give informed consent and, when applicable, minor assent prior to any study-related procedures or change in treatment. The patient/legally authorized representative must also give authorization (US only), data protection consent (Europe only), and other written documentation in accordance with the relevant country and local privacy requirements (where applicable) prior to any study-related procedures or change in treatment.

Further information is provided in Section 10.1.

Each patient who provides informed consent and/or assent will be assigned a patient number that will be used on patient documentation throughout the study.

8.2 Procedures for Final Study Entry

At visit 3 (randomization) patients must meet all of the inclusion criteria and must not meet any of the exclusion criteria. Also, all females of childbearing potential must have a negative urine pregnancy test.

The patient is considered to have entered this study at the time of randomization to treatment on day 1. See Section 5.5 for the method for assignment to treatment groups/randomization.

8.3 Visits and Associated Procedures

Ideally, the CGI by Physician should be performed prior to administering the MAS-B and MTS to reduce the likelihood of the CGI being influenced by the spasticity evaluations. An alternative is to have different evaluators rate the CGI and perform the spasticity assessments (MAS-B and MTS). Whenever possible each procedure should be performed by the same evaluator for an individual patient throughout the trial. Study personnel should avoid reviewing or discussing the MAS-B, MTS, or CGI scores from previous visits when they are completing these assessments.

In addition to the procedures outlined below, patients are to complete approximately 1-hour weekly standardized OT sessions (see Section 4.5.3) from week -2 through week 11.

8.3.1 Visit 1: 2 to 4 Weeks Before Day 1 (Screening)

- Obtain written informed consent and minor assent and data protection from the patient and/or legally authorized representative prior to performing any study-related procedures.
- Obtain patient identification number from the IVRS/IWRS.
- Obtain demographic information, including date of birth. Ensure that the patient will be ≥ 2 years and ≤ 16 years and 11 months (prior to 17th birthday) on projected day 1, randomization visit.
- Obtain medical and surgical history, ensuring that the patient has upper limb monoplegic, hemiplegic, or triplegic spasticity with single-arm sparing resulting from cerebral palsy, or is post-stroke with the stroke onset prior to age 2 and at least 12 months prior to the day 1 visit. Include details on histories of dysphagia, drooling, aspiration pneumonia, seizure, and epilepsy.
- Obtain past (in the last 3 months) and current concomitant medication use (including prescription, non-prescription, and herbal medications) and procedures. Previous use of botulinum toxin, phenol, and alcohol injections should be included.
- Perform C-SSRS (for patients ≥ 6 years of age at day 1).
- Perform physical examination, including measurement of height and weight.
- Obtain vital signs (blood pressure, pulse rate, respiratory rate, and body temperature).
- Perform ECG.
- Collect blood sample for hematology, serum chemistry, and HbA1c analysis after informed consent is signed. Fasting blood samples should be collected unless the

patient is not able to fast for approximately 8 hours. Patients who are willing to fast and did not come to the visit in a fasting state may return prior to the day 1 visit for blood sample collection as long as the laboratory results can be received and reviewed at or before the day 1 visit.

- Perform urine pregnancy test for all females of childbearing potential.
- Discuss choice of contraceptive method with female patients of childbearing potential and/or their caregivers and document method of contraception in the source documentation and the eCRF. Counsel such female patients/caregivers regarding the importance of maintaining their agreed upon method of contraception throughout the study.
- Ascertain spasticity only in the study upper limb using the HAT.
- Assess dystonia only in the study upper limb using the BAD scale.
- Assess manual ability only in the study upper limb using the MACS.
- Assess gross motor function using the GMFCS-E&R.
- Assess spasticity in the elbow, wrist, and finger in the study limb using the MAS-B.
- Perform MTS in the elbow, wrist, and finger in the study limb. Passive range of motion for the elbow, wrist, and finger for can be performed during the MTS assessment in order to verify inclusion criteria.
- Evaluate inclusion and exclusion criteria.
 - For patients who are not eligible for the study (screen failures), depending on the reason(s) for screen failure, collect detailed information regarding spasticity, contracture, respiratory condition or functions associated with increased risk of aspiration, seizure, and epilepsy.
- Query patient for any adverse event that has occurred and any related medication used or procedure performed since signing the informed consent.
- Instruct patient/caregiver to initiate approximately 1-hour weekly standardized OT session with the therapist at week -2 and schedule through the last session at week 11.
- Schedule the next visit, if applicable.

8.3.2 Visit 2: Week -2 (OT Start) – Visit with the Occupational Therapist

- Establish with each patient/caregiver 2 goals for the GAS (1 functional active and 1 functional passive) and define each level of patient-specific goal achievement for each of the 2 goals using the GAS by Physician.

- With the patient/caregiver, review protocol-specified standardized weekly OT and develop a patient-tailored OT plan.
- If patient reports adverse events to the therapist, the therapist should inform the Study Coordinator for further follow-up regarding adverse events and related medication used or procedures performed.
- Schedule the next weekly OT session.

8.3.3 Visit 3: Day 1 (Randomization/Treatment)

- The following procedures must be performed prior to the study treatment:**
 - [REDACTED]
 - Note any update to medical and surgical history, if needed. Query patient/caregiver for any adverse events prior to study treatment.
 - Perform C-SSRS (for patients \geq 6 years of age at day 1).
 - For patients who are not eligible for the study (screen failures), depending on the reason(s) for screen failure, collect detailed information regarding spasticity, contracture, respiratory condition or functions associated with increased risk of aspiration, seizure, and epilepsy.
 - Obtain any update to concomitant medication use.
 - Obtain any information on new medical procedures or tests since the last visit.
 - Obtain vital signs (blood pressure, pulse rate, respiratory rate, and body temperature).
 - Obtain weight in kilograms.
 - Review the results of the screening safety laboratory tests.
 - Perform urine pregnancy test for all females of childbearing potential.
 - Assess spasticity in the elbow, wrist, and finger in the study limb using the MAS-B.
 - Perform MTS in the elbow, wrist, and finger in the study limb. Passive range of motion for the elbow, wrist, and finger can be performed during the MTS assessment in order to verify inclusion criteria.
 - Confirm the 2 goals selected and the definitions of patient-specific goal achievement using the GAS by Physician.

- [REDACTED]
- If applicable, counsel female patients and/or caregivers of childbearing potential regarding the importance of maintaining their agreed upon method of contraception throughout the study.
- Confirm patient continues to meet study inclusion and exclusion criteria.
- Identify principal muscle group and calculate the dose for study treatment using the dose calculation worksheet and dose verification eCRF.
- Access the IVRS/IWRS to randomize the patient and obtain a study medication kit number.
- Inform IDR that patient is qualified for the study treatment and send blinded dosing summary to the IDR for study drug preparation.
- Inject assigned study treatment as per protocol (see Section 5.9).
- Query patient/caregiver for any adverse events and related medication used or procedure performed.
- Remind patient/caregiver of the importance of the weekly OT session.
- Schedule the next visit.

8.3.4 Visits 4, 5, 6, and 7: Weeks 2, 4, 6, and 8 (Follow-up Visits)

- [REDACTED]
- [REDACTED]
- [REDACTED]
- [REDACTED]
- Query patient/caregiver for any adverse events.
- Perform C-SSRS (for patients \geq 6 years of age at day 1).
- Obtain any update to concomitant medication use.
- Obtain any information on new medical procedures or tests since the last visit.
- Rate the CGI by Physician before performing the spasticity assessments (MAS-B and MTS).
- Assess spasticity in the elbow, wrist, and finger in the study limb using the MAS-B.
- Perform MTS on the elbow, wrist, and finger in the study limb.
- Only at visit 7/week 8, evaluate the patient's performance for each of the 2 goals using the GAS by Physician.

- [REDACTED]
- [REDACTED]
- Remind patient/caregiver of the importance of the weekly OT session.
- Schedule the next visit.

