8.3.5 Visit 8: Week 12 or Early Termination (Exit Visit)

- [REDACTED]
- [REDACTED]
- [REDACTED]
- Query patient/caregiver for any adverse events.
- Perform C-SSRS (for patients \geq 6 years of age at day 1).
- Obtain any update to concomitant medication use.
- Obtain any information on new medical procedures or tests since the last visit.
- Perform physical examination, including measurement of weight.
- Obtain vital signs (blood pressure, pulse rate, respiratory rate, and body temperature).
- Collect blood sample for hematology, serum chemistry, and hemoglobin A1c analysis for all patients. Fasting blood samples should be collected unless the patient is not able to fast for approximately 8 hours.
- Perform urine pregnancy test for all females of childbearing potential.
- Rate the CGI by Physician before performing the spasticity assessments (MAS-B and MTS).
- Assess spasticity in elbow, wrist, and finger in the study limb using the MAS-B.
- Perform MTS on the elbow, wrist, and finger in the study limb.
- Evaluate the patient's performance for each of the 2 goals using the GAS by Physician.
- [REDACTED]
- [REDACTED]
- Any adverse event that is marked "ongoing" at the exit visit must be followed-up as appropriate.
- Enter patient exit status in the IVRS/IWRS.
- If the patient/legally authorized representative agrees to participate in the follow-on Study 191622-105, have the patient/legally authorized representative sign the consent/assent/privacy form and proceed with the day 1 visit for that study.

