12.1.12 Goal Attainment Scale (GAS) by Physician

The GAS by Physician will be used to measure functional goal attainment relative to the effect of the study intervention. Goals should be specific, measurable, achievable and realistic, resource sensitive, and timed (SMART). At week -2, two goals will be selected by the patient and family in consultation with the physician investigator and/or treating therapist relative to the upper limb impairment due to spasticity. These goals will be confirmed at the day 1 visit. Two functional goals will be established for each patient: a functional active goal and a functional passive goal. After the functional goals (active and passive) are set, they should remain the same throughout the study. It is crucial to define all the levels of the goal. Goal achievement will be assessed by the physician investigator taking into consideration input from the treating therapist, caregiver, and/or patient.

The following scale will be used to evaluate the level of achievement of the 2 goals:

- 3 Worse than start
- 2 Equal to start: the patient's initial condition; no change
- 1 Less than expected: slight improvement, but below the defined therapeutic goal
- 0 Expected goal: attains the defined therapeutic goal
- +1 Somewhat more than expected: improvement slightly exceeds the defined therapeutic goal
- +2 Much more than expected: improvements clearly exceed the defined therapeutic goal

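### At weeks 8 and 12 the protocol permits, but does not require, the physician-rated GAS to be scored just after tone has been assessed, an influence it guards against for the CGI

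*Protocol*

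**What the plan says.** The GAS is rated at weeks 8 and 12. In Protocol 8.3.4 (follow-up visits) the visible efficacy bullets run CGI, MAS-B, MTS and then GAS, the last worded as "Only at visit 7/week 8, evaluate the patient's performance for each of the 2 goals using the GAS by Physician". In 8.3.5 (week 12 or early termination) the order is the same, ending with "Evaluate the patient's performance for each of the 2 goals using the GAS by Physician".

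Both lists tell sites to rate the CGI ahead of the spasticity assessments. Section 8.3, repeated in 12.1.15, gives the reason: "Ideally, the CGI by Physician should be performed prior to administering the MAS-B and MTS to reduce the likelihood of the CGI being influenced" by those evaluations. The same two sections offer separate evaluators for the CGI and the tone measures as an alternative. They add a third rule: "Study personnel should avoid reviewing or discussing the MAS-B, MTS, or CGI scores from previous visits" while completing these assessments. None of the three rules mentions the GAS.

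Section 12.1.12 says who rates it: "Goal achievement will be assessed by the physician investigator taking into consideration input from the treating therapist, caregiver, and/or patient". That section sets no order relative to MAS-B or MTS and asks for no separate rater. The SAP (5.1 and 5.3.3) describes how the GAS is derived and analysed and is silent on both matters.

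**The concern.** The sponsor recognised that someone who has just felt the limb's tone may carry that impression into a judgement rating. The Amendment 1 summary (12.4) says the emphasis on assessment order was increased to limit potential bias. The GAS is also a physician's judgement, made on the same child at the same visit, and the documents give no reason for leaving it out.

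Blinding to assignment does not fully answer this. If BOTOX lowers tone at weeks 8 and 12, the tone just felt is correlated with treatment even for a blinded rater. Any pull of the GAS towards that finding would then tend to favour the BOTOX arms. SAP 5.3.3 also analyses GAS responders at two cut-offs, 0 or higher and -1 or higher. A one-level shift from -2 (no change) to -1 (slight improvement), or from -1 to 0 (goal attained), would change a patient's responder status.

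**Working it through.** No arithmetic settles this point, so the check is to set the provisions for the two physician ratings side by side.

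| Item | CGI by Physician | GAS by Physician |
|---|---|---|
| Rater | Physician investigator (12.1.15) | Physician investigator, with input from others (12.1.12) |
| Rated at | Weeks 2, 4, 6, 8, 12 | Weeks 8, 12 |
| Place in visit lists (8.3.4, 8.3.5) | Before MAS-B and MTS | After MAS-B and MTS |
| Explicit order instruction | Yes (8.3, 8.3.4, 8.3.5, 12.1.15) | None found |
| Separate-evaluator option | Yes (8.3, 12.1.15) | None found |
| Named in the prior-score rule | Yes | No |
| Basis of rating | Open global judgement, -4 to +4 | Patient-specific levels, -3 to +2, set at week -2 and confirmed on day 1 |

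1. *Is the exposed order allowed?* Yes. A site that works down the list at week 8 or 12 rates the GAS after MAS-B and MTS, and no sentence found tells it otherwise.

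2. *Is it required?* No. The lists are not declared to be a sequence. The GAS may be rated first, or by someone who did not assess tone.

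3. *Which results could be touched?* The GAS at weeks 8 and 12 only. The primary endpoint, and the co-primary pair for the US FDA, use MAS-B and CGI at weeks 4 and 6, when no GAS is rated.

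4. *Can the effect be sized?* A simple form would be: shift in the GAS difference = (GAS points moved per MAS-B grade felt) × (MAS-B difference between arms at that visit). The documents do not give the first factor. For the second, Table 4 has only -0.5, planned for the average of weeks 4 and 6; nothing is planned for weeks 8 and 12. No standard deviation is given for the GAS, so a shift in points could not be judged large or small either. The power figures in 7.5 (86% for MAS-B, 94% for CGI, 81% jointly) do not depend on the GAS and would not change if it were moved.

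**The case against.** The strongest reply is that bullet order is not a mandated sequence. Where order matters the protocol says so: CGI before the spasticity assessments, R1 before R2 in 12.1.11, and the day 1 procedures that must precede treatment in 8.3.3. A reader might infer that sites are directed to rate the GAS after feeling tone. The text does not support that; it leaves the order open. What remains is that, for the CGI, the sponsor did not rely on an open order.

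Second, the GAS leaves less room for a halo than the CGI. The CGI may weigh side effects, risk/benefit and social status. The GAS is scored against levels defined for the individual patient before treatment and then kept fixed, with input from the therapist, caregiver or patient. This stands as mitigation, but the physician still assigns the level.

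Third, separation may already occur. If a site uses a different evaluator for the CGI and the same physician rates the GAS, both ratings are protected. The Amendment 2 summary (12.5) notes that other qualified site personnel can perform the MAS-B. This depends on site practice and is not secured by any rule.

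Fourth, the CGI order is itself only an ideal in 8.3 and 12.1.15. That is so, although the visit lists put it as an instruction, and the GAS has neither.

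Finally, Table 1 with its footnotes and the Study Procedure Manual could not be consulted, so a GAS rule there cannot be excluded. The amendment log describes Table 1 footnote i only in terms of the CGI and the spasticity assessments.

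**Conclusion.** The gap is real and minor. The protocol permits, without requiring, the GAS to be rated by someone who has just assessed tone at that visit, and it protects the CGI against this same influence. The mitigations reduce the influence but do not remove it.

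Two stronger readings go beyond the documents. One is that part of any GAS difference would be the tone result counted again. That needs evidence that raters are in fact influenced, and that they rate in the exposed order. It also treats the GAS as meant to be independent of tone. Section 12.1.12 says only that it measures functional goal attainment relative to the effect of the intervention, on goals tied to impairment from spasticity. The other is a numerical bias derived from the planned 0.5-grade MAS-B difference. That figure belongs to weeks 4 and 6, and the multiplier would have to be invented.

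The size is therefore unknown. The conclusion rests on the visible text of 8.3 to 8.3.5, 12.1.12 and 12.1.15, and on no contrary instruction standing in Table 1 or the manual. It bears on one secondary endpoint and on no primary or co-primary inference.

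**What to change.** - In 8.3.4 (week 8) and 8.3.5, move the GAS bullet to follow the CGI and precede MAS-B and MTS, with the same explicit instruction to rate it before the spasticity assessments that the CGI bullet carries.
- In 8.3 and 12.1.15, extend the ordering, separate-evaluator and prior-score sentences to the GAS. The prior-score rule matters because a physician who also rates tone has felt it at weeks 2, 4 and 6, and re-ordering week 8 alone does not address that. The wording should leave the rater free to consult the predefined goal levels.
- Add a matching sentence to 12.1.12.
- Align Table 1 footnote i if needed.

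The cost is two moved bullets, a few edited sentences in two sections and one added sentence. No assessment or visit is added, and the SAP, the sample size and the week 4 and 6 assessments stay as they are. The separate-evaluator route remains an option, so no extra staff are needed.

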8.3.5 Visit 8: Week 12 or Early Termination (Exit Visit)

- [REDACTED]
- [REDACTED]
- [REDACTED]
- Query patient/caregiver for any adverse events.
- Perform C-SSRS (for patients \geq 6 years of age at day 1).
- Obtain any update to concomitant medication use.
- Obtain any information on new medical procedures or tests since the last visit.
- Perform physical examination, including measurement of weight.
- Obtain vital signs (blood pressure, pulse rate, respiratory rate, and body temperature).
- Collect blood sample for hematology, serum chemistry, and hemoglobin A1c analysis for all patients. Fasting blood samples should be collected unless the patient is not able to fast for approximately 8 hours.
- Perform urine pregnancy test for all females of childbearing potential.
- Rate the CGI by Physician before performing the spasticity assessments (MAS-B and MTS).
- Assess spasticity in elbow, wrist, and finger in the study limb using the MAS-B.
- Perform MTS on the elbow, wrist, and finger in the study limb.
- Evaluate the patient's performance for each of the 2 goals using the GAS by Physician.
- [REDACTED]
- [REDACTED]
- Any adverse event that is marked "ongoing" at the exit visit must be followed-up as appropriate.
- Enter patient exit status in the IVRS/IWRS.
- If the patient/legally authorized representative agrees to participate in the follow-on Study 191622-105, have the patient/legally authorized representative sign the consent/assent/privacy form and proceed with the day 1 visit for that study.

